# 8.3.2.1 Criteria for Changing Postoperative Adjuvant Chemotherapy

[1] Criteria for postponing all postoperative adjuvant chemotherapy drugs

Referring to the criteria in Table 8.3-3 before administration on the day of postoperative adjuvant chemotherapy administration in course 2 and beyond, the investigator or subinvestigator will postpone the administration of all postoperative adjuvant chemotherapy drugs until the subject's condition satisfies the criteria. The administration of all drugs may be postponed if any of the criteria for suspending oxaliplatin in Table 8.3-5 are satisfied on the day scheduled for oxaliplatin administration. If no postoperative adjuvant chemotherapy for the subsequent course is begun within 43 days of the start of the most recent postoperative adjuvant chemotherapy (Day 1), the subject will be discontinued from the study and undergo the end-of-study evaluations.

Table 8.3-3 Criteria for postponing all postoperative adjuvant chemotherapy drugs

Туре	Initiation criteria
Neutrophil count	$\geq 1,500/\text{mm}^3$
Platelet count	$\geq$ 75,000/mm 

[2] Criteria for reducing the dose of oxaliplatin and fluorouracil in association with adverse events

If a subject experiences an adverse event, the investigator or subinvestigator will reduce the dose
of oxaliplatin and fluorouracil in reference to the following criteria:

Table 8.3-4 Criteria for reducing the dose of oxaliplatin and fluorouracil in association with adverse events

Туре	Greatest severity	Next dose
Neutrophil count	<500/mm 	Reduce oxaliplatin dose to 75 mg/m 
Platelet count	<50,000/mm 	Reduce fluorouracil dose by 20%
Gastrointestinal tract adverse	≥Grade 3 a)	
events (occurring despite		
prophylactic treatment)		

a) NCI-CTCAE

- [3] Criteria for suspending or reducing the dose of oxaliplatin in association with peripheral neuropathy

  The investigator or subinvestigator will determine the dose of oxaliplatin according to the criteria
  in Table 8.3-5 on Day 1 of each course.
  - If reducing the oxaliplatin dose, do not increase the dose even if the CTCAE grade improves.
  - After suspending oxaliplatin, resume treatment at the dose of 75 mg/m².
     The investigator or subinvestigator need not comply with these criteria when determining that other criteria are necessary to ensure subject safety.

Table 8.3-5 Criteria for suspending or reducing the dose of oxaliplatin in association with peripheral neuropathy

Greatest NCI-CTCAE*1 grade after previous oxaliplatin dose	Day 1 NCI-CTCAE grade (day of evaluation)	Action to take for oxaliplatin
≤Grade 1	≤Grade 1	Do not reduce dose or suspend.
≥Grade 2	≤Grade 1	Do not reduce dose or suspend.  (The dose may be reduced to 75 mg/m  .)
Any	Grade 2	Reduce the dose to 75 mg/m  .  (Treatment may be suspended.)
Any	≥Grade 3	Treatment may be suspended.

\*1 Assess the NCI-CTCAE grade of the more severe of peripheral motor neuropathy or peripheral sensory neuropathy.

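### The oxaliplatin dosing table requires a reduction to 75 mg/m² at Day 1 Grade 2 neuropathy but only permits suspension, with no dose named, at Day 1 Grade 3 or worse

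*Protocol*

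**What the plan says.** Protocol Section 8.3.2.1 [3] states that the investigator or subinvestigator "will determine the dose of oxaliplatin according to the criteria" in Table 8.3-5, on Day 1 of each course. The grade used is the worse of motor and sensory neuropathy. The table's entries are:

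- **Day 1 Grade 1 or lower:** "Do not reduce dose or suspend". If the worst grade since the previous dose was 2 or more, a reduction to 75 mg/m² is allowed as an option in parentheses.
- **Day 1 Grade 2, any earlier grade:** "Reduce the dose to 75 mg/m"², with suspension as an option in parentheses.
- **Day 1 Grade 3 or worse, any earlier grade:** "Treatment may be suspended". Nothing else is entered.

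Four rules in the same section bear on the row:

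- No re-escalation: "If reducing the oxaliplatin dose, do not increase the dose even if the CTCAE grade improves".
- Dose after a suspension: "After suspending oxaliplatin, resume treatment at the dose of 75 mg/m"².
- Safety override: the investigator "need not comply with these criteria when determining that other criteria are necessary to ensure subject safety".
- Postponement, in item [1]: "The administration of all drugs may be postponed if any of the criteria for suspending oxaliplatin in Table 8.3-5 are satisfied" on the scheduled day.

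**The concern.** A toxicity-driven dosing rule should be at least as strict at a higher grade as at a lower one. Here Grade 2 carries an instruction and a dose, while Grade 3 or worse carries only a permission and no dose. Section 1.1.3 says the risk of chronic oxaliplatin neuropathy rises with cumulative dose and that symptoms may last months or years after treatment, so this is first a matter of patient safety.

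There is also a small effect on efficacy endpoint [6]. Section 12.6.2.6 defines a composite event of discontinuation, suspension or dose reduction due to CIPN. A subject at 85 mg/m² with Day 1 Grade 2 becomes an event because the table requires it. The same subject at Grade 3 or worse becomes an event only if the investigator chooses to act, so differing site practice could enter the endpoint at the severe end.

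**Working it through.** The protocol states no figure to reproduce. The check is a reading of the rules, followed by simple arithmetic on the dose.

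**Does another rule supply the missing dose?** Take a subject still on 85 mg/m² who is Grade 3 or worse on Day 1.

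- The no-re-escalation rule applies only after a reduction. This subject has not been reduced.
- The 75 mg/m² resumption rule applies only after a suspension. This subject has not been suspended.
- Postponement of all drugs is optional and names no dose. Table 8.3-2 defines postponing separately from suspending and reducing, so a subject whose course was postponed for neuropathy is not brought under either 75 mg/m² rule.
- The safety override is discretionary and names no dose.
- Table 8.3-4 covers neutrophils, platelets and gastrointestinal events, not neuropathy.
- Section 9.7.4.1 does not count CIPN as an adverse event, so the adverse-event discontinuation criterion in Section 11.2.1 [1] is not a clear backstop.
- Section 11.2.1 [4] (lack of efficacy) and [6] (investigator decision) allow discontinuation, but grade alone triggers neither.

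No rule fixes a dose for this subject. Equally, the table does not endorse full dose: where it wants no change it says so, and the Grade 3 row does not.

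**Who is exposed?** Mainly subjects who go from Day 1 Grade 1 or lower to Day 1 Grade 3 or worse between consecutive courses, 14 days apart on schedule. A second route is a subject at 85 mg/m² whose course was postponed for neuropathy and who is Grade 3 or worse when it starts. Subjects already at 75 mg/m² have an excess of 75 − 75 = 0.

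**How large is the excess?** Inputs are 85 mg/m² per course (Section 8.3.1), 12 courses (Section 8.1.2) and the reduced dose of 75 mg/m² (Table 8.3-5).

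- Per course: 85 − 75 = 10 mg/m², and 10/85 = 11.8% of the course dose.
- Planned total: 12 × 85 = 1,020 mg/m², and 10/1,020 = 1.0%.

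The protocol gives no frequency or timing for unreduced Day 1 Grade 3 neuropathy. As an illustration only, assume it first occurs at course 8 to 12 and that every course from then on is given at 85 mg/m²:

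| First such course | Courses at 85 mg/m² | Excess (mg/m²) | Share of 1,020 |
|---|---|---|---|
| 8 | 5 | 5 × 10 = 50 | 4.9% |
| 12 | 1 | 1 × 10 = 10 | 1.0% |

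**The case against.** The strongest reply is that this is a loosely worded suspension row. In the two rows that have a parenthesis, the action stands outside it and the option inside. At Grade 3 suspension moves outside and becomes the only listed action, so the table escalates from no change, to reduce, to suspend. Item [1] of the section refers to criteria for suspending oxaliplatin in this table, and the resumption rule then gives 75 mg/m², so on this reading no dose is missing. The rationale in Section 8.4.2 also says that Grade 2 or greater neuropathy calls for considering reduction or suspension. That reading is plausible and may be what was meant. But the printed verb is the same permissive one the table uses for its options, and the Section 8.4.2 remark explains a concomitant-medication rule and sets no dose. Two careful sites could act differently.

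A second reply is that the remaining case is small. That stands. Harm needs an investigator who sees Grade 3 with suspension as the only listed action and still gives 85 mg/m². The 50 mg/m² illustration is an upper case: the table is reapplied each course, so a later Day 1 at Grade 2 would require the reduction and bar re-escalation. The firm figure is 10 mg/m² per affected course.

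A third reply is that the study is exploratory, has no primary endpoint, and applies the rule identically to blinded arms. This limits the statistical consequence but does not answer the safety point.

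Finally, choosing between a 75 mg/m² cap and mandatory suspension is a clinical decision that the protocol does not settle. That is right, and the correction should leave it to the sponsor's clinical team.

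**Conclusion.** The point holds. As printed, Table 8.3-5 requires a reduction at Day 1 Grade 2 and requires nothing at Day 1 Grade 3 or worse, where it also names no dose if treatment is not suspended. This conclusion rests on the literal wording. Whether mandatory suspension was intended cannot be decided from the protocol.

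The size is modest: 10 mg/m² for each affected course, confined mainly to subjects not yet reduced or suspended, with the number of such subjects unknown. The effect on endpoint [6] is small, and no sample size or analysis method changes. It should be fixed because it is an ambiguity in a patient-safety dosing rule and is cheap to remove.

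**What to change.** Amend the Grade 3 or worse row so that suspension stays optional but any oxaliplatin given is reduced to 75 mg/m². If the sponsor's clinical team confirms that suspension was meant to be mandatory, the row should instruct suspension outright. Keep the safety override and the option to postpone all drugs in either case.

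The cost is one table row in a protocol amendment, with no change to visits, data collection or sample size. The cap takes away a little investigator discretion. Mandatory suspension costs more: under Section 8.1.4 the investigational product is withheld whenever oxaliplatin is suspended, and it sits less well with the aim in Section 5.2.1 [6] of keeping adequate chemotherapy going. For that reason the cap is the better default unless the sponsor states otherwise.

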# 8.4 Prohibited Treatments and Interventions During the Study

# 8.4.1 Prohibited Concomitant Drugs

- ➤ The administration of the following medications is prohibited from informed consent until study completion.
  - (1) Other investigational products
  - (2) Thrombomodulin alfa (recombinant)
  - (3) Antineoplastic agents other than those specified for use in the postoperative adjuvant chemotherapy in this study

#### Rationale

- (1) Out of concern for subject safety.
- (2) This is the active ingredient of the investigational medicinal product and would not allow proper evaluation of efficacy and safety.
- (3) The use of these drugs could induce drug-induced peripheral neuropathy, which would prevent proper evaluation of efficacy. Adding other antineoplastic agents, moreover, would affect the safety evaluation of Recomodulin.
- > The administration of the following medications is prohibited from the start of administration of the investigational product until study completion.
  - (1) Thrombolytic drugs (e.g., t-PA preparations, urokinase)

#### Rationale

• (1) Out of concern for subject safety because the pharmacological action of the investigational medicinal product could increase the risk of bleeding.

# 8.4.2 Restricted Concomitant Drugs

Over-the-counter medications and ready-made transfusion preparations are not considered restricted concomitant medications.

> The administration of the following medications is prohibited from informed consent until study completion except in association with use while peripheral motor neuropathy or peripheral sensory

neuropathy is found by the investigator or subinvestigator to be Grade 2 or greater based on NCI-CTCAE.

- (1) Calcium gluconate, magnesium sulfate
- (2) Glutathione
- (3) L-glutamine
- (4) Vitamin B6, B12, and E preparations
- (5) Goshajinkigan, shakuyaku-kanzoto
- (6) Narcotics and similar drugs (including the opioid receptor agonist codeine phosphate)
- (7) Oral and injected adrenocorticosteroids (except when used to treat nausea/vomiting associated with the administration of an antineoplastic agent or to treat an allergy)
- (8) Pregabalin, gabapentin
- (9) Nonsteroidal anti-inflammatory drugs (NSAIDs, except when used for a purpose other than CIPN treatment)
- (10) Tricyclic antidepressants
- (11) Serotonin/noradrenaline reuptake inhibitors

#### Rationale

- For ethical reasons, prohibitions of these medications are lifted because NCI-CTCAE Grade 2 or greater peripheral motor neuropathy or peripheral sensory neuropathy is of a severity requiring consideration of oxaliplatin dose reduction/suspension.
- (1) to (5) These drugs are reported to be effective in the prevention or treatment of CIPN, meaning that their use would prevent proper evaluation of efficacy.
- (6) to (11) These drugs may be effective in the treatment of CIPN, meaning that their use would prevent proper evaluation of efficacy.
- ➤ Initiating the administration of or increasing the dose of any of the following medications is prohibited from informed consent until study completion. Subjects may continue to use the medications that they had been using before informed consent provided that no dose changes are made. (Dose reductions are allowed.)
  - (1) Isoniazid, ethambutol, metronidazole, medications for the treatment of HIV infection, HMG-CoA reductase inhibitors, tacrolimus, colchicine, and interferon preparations

# Rationale

• (1) These drugs could induce drug-induced peripheral neuropathy. Initiation or dose escalation during the study could affect efficacy evaluation.

# 8.4.3 Prohibited Concomitant Therapies

- > The following treatments are prohibited from informed consent until study completion.
  - (1) Radiotherapy
  - (2) Operations and other surgical procedures that could affect efficacy evaluation *Rationale* 
    - (1) Because of the potential impact on the evaluation of safety.
    - (2) Because of the impact on properly evaluating subject efficacy.

# 9. Investigations/Observations and Evaluations

The investigator or subinvestigator will perform the investigations/observations and evaluations specified in this section. The investigator or subinvestigator or a clinical research coordinator will complete electronic case report forms (eCRFs) based on the source documents.

# 9.1 Investigation/Observation and Evaluation Schedule

The time points for investigations/observations are shown in Table 9.1-1, Summary of study schedule. Hereafter, time points are indicated with the first day of postoperative adjuvant chemotherapy in each course counted as Day 1 (D1).

Table 9.1-1 Summary of study schedule

							- 1	abic	9.1-	I Sui	IIIIII	il y Oi	Stuc	ly SC	leuu	IC											
	Screening period													Follow-up period h)													
	-	Course 1									Courses 2 to 11 Course 12														01224		luatio
Test/observation schedule		. 8 5	Investigational product product administration		D2	D3			D29	prece	Investigational product product administration	urse)	D2 a)	D3 a)	D8	D15	D29	prece	Investigational product product administration	urse)	D2 a)	D3 a)	D8	D15	At discontinuation of the treatment 	At study completion (d43 of the last course) 	Unscheduled CIPN evaluation
Permitted window of time from the specified date (days)	d-14 to d-1				-		T.	+7	+7		d43 of eding co		4	-	4	+7	+7		d43 of eding co		-	-	-	+7	×	+14	-
Written informed consent	•										Š		\$1 10	9	5	- 20	24 28							j			
Subject demographic information survey	•	•																									
Patient registration, randomization		•																									
Office visit			•		•	•		0	0		•		•	•	2 2	0	0		•		•	•		•	•	•	•
Weight measurement		•k)								•k)	Š		21	3	5	, j.,	24 28	•k)									
Investigational product administration			•		•	•					•a)		•	•					•a)		•	•					
Investigational product administration status survey			•		•	•		0	0		•		•	•		0	0		•		•	•					
Postoperative adjuvant chemotherapy				←								+		1		10	208			+		$\rightarrow$					
Postoperative adjuvant chemotherapy status survey				•	•1)	•0		0	0			•	•0	•)		0	0			•	•j)	•0					
Concomitant medications/concomitant therapies survey	←									1950**				N N		-	2							→	•	•	
Pregnancy test										• d)				200			50									•	
NCI-CTCAE					•			0	0				•	•		0	0				•	•		•	•	•	
DEB-NTC		•						0	0	•						0	0	•						•	•	•	
FACT/GOG-NTX-12		•					•	0	0	•					•	0	0	•					ě	•	•	•	
FACT-G		•								•e)			, and											•	•	•	
NRS (pain)	Š.	•					•	0	0	•			20	1	•	0	0	•					•	•	•	•	

	Laboratory tests	•°)						• k)					• k)				•	•	•	
ety	Vital signs	•						•					•				•	•	•	
Saf	Adverse events	lacksquare															→	•	•	
	Immunogenicity		•																•	
Ph	armacokinetics		•	• f)	• f)	• f)				$\Delta^{f)}$	$\Delta^{f)}$				$\Delta^{f)}$	$\Delta^{f)}$				

Time points are expressed as "Day (D)," and numbers of days are expressed as "day (d)."

- •: required
- : to be performed only in the event of postponement of the administration of all drugs for postoperative adjuvant chemotherapy
- Δ: if no blood samples are available from course 1, perform once in one of the courses from 2 to 12
- a) Not required in courses in which oxaliplatin is suspended
- b) To be performed before investigational product administration if the evaluation takes place on the same day as investigational product administration
- c) To be performed between Day -7 and Day -1 (1 day before registration); hepatitis B test data obtained within 6 months before the day of registration may also be used
- d) To be performed only in course 2; may be determined on the day before Day 1
- e) To be performed only in courses 5 and 9
- f) Collect blood samples immediately after and from 30 to 120 minutes after completion of investigational product administration
- g) If the evaluation at treatment period discontinuation takes place on or after Day 43 of the last course of postoperative adjuvant chemotherapy, or if the tests/observations for the subsequent clinical study are not possible, perform the end-of-study evaluations instead of the treatment-period discontinuation evaluations. If the course 12 postoperative adjuvant chemotherapy has not commenced within 34 weeks (Day 239 from the day of registration), discontinue the subject from the study, perform the treatment-period discontinuation evaluations, and then perform the end-of-study evaluations on Day 43 of the last course of postoperative adjuvant chemotherapy.
- h) If any postoperative adjuvant chemotherapy for the subsequent course has not commenced by Day 43 of a course, discontinue the subject from the study and perform the end-of-study evaluations.
- i) If the subject is discontinued from the study in the follow-up period, perform the end-of-study evaluations.
- j) Determine the status of fluorouracil continuous intravenous infusion use.
- k) May be determined on the day before Day 1

# 9.2 Investigations/Observations and Evaluations to be Conducted at Each Time Point

# 9.2.1 Screening Period (Day -14 to Day -1)

- Informed consent
- Subject demographic information survey
- Initiation of a survey on concomitant medications/therapies
- Initiation of a survey on adverse events
- Pregnancy test (only subjects for whom the test is required)
- Vital sign measurement
- Laboratory tests (blood/urine)\*1
  - \*1 To be performed between Day -7 and Day -1 (1 day before registration)

# 9.2.2 Treatment Period\*1

\*1 If any postoperative adjuvant chemotherapy for the subsequent course has not commenced by Day 43 of a course, discontinue the subject from the study and perform the study completion evaluations.

# 9.2.2.1 Day 1 of Course 1

- ➤ Before investigational product administration
  - Subject demographic information survey
  - · Laboratory test results verification
  - Patient registration
  - · Concomitant medications/therapies survey
  - Adverse events survey
  - Efficacy endpoints survey
    - NCI-CTCAE: As of the time of evaluation
    - DEB-NTC
    - FACT/GOG-NTX-12
    - FACT-G
    - NRS (pain)
  - Blood sampling for pharmacokinetic analysis
  - Blood sampling for immunogenicity test
  - Weighing of subject to determine investigational product dose\*1
- > Investigational product administration and administration status survey
- > After investigational product administration
  - Postoperative adjuvant chemotherapy administration and administration status survey
  - Blood sampling for pharmacokinetic analysis
  - Adverse events survey
    - \*1 Subjects may be weighed on the previous day

# 9.2.2.2 Days 2 and 3 of Course 1

- ➤ Before investigational product administration
  - · Concomitant medications/therapies survey
  - · Adverse events survey

- Efficacy endpoint survey
  - NCI-CTCAE: The worst condition noted between the preceding evaluation (excluding any unscheduled evaluation) and the day of evaluation
- > Investigational product administration and administration status survey
- > Fluorouracil continuous intravenous infusion status survey
- > After investigational product administration
  - Blood sampling for pharmacokinetic analysis
  - · Adverse events survey

# 9.2.2.3 Day 8 of Course 1\*1

- Efficacy endpoint survey
  - FACT/GOG-NTX-12
  - NRS (pain)
  - \*1 No office visit required. The survey may be performed when the subject is at home or elsewhere.

# 9.2.2.4 Day 15 (permitted window, +7 days)\*1 and Day 29 (permitted window, +7 days)\*1 of Course 1

- · Concomitant medications/therapies survey
- · Adverse events survey
- · Investigational product administration status survey
- · Postoperative adjuvant chemotherapy administration status survey
- Efficacy endpoint survey
  - NCI-CTCAE
    - i) The worst condition noted between the preceding evaluation (excluding any unscheduled evaluation) and the day of evaluation
    - ii) Condition at the time of evaluation
  - DEB-NTC
  - FACT/GOG-NTX-12
  - NRS (pain)
  - \*1 To be performed only in the event of postponement of the administration of all drugs for postoperative adjuvant chemotherapy

# 9.2.2.5 Day 1 of Courses 2 to 12

- > Before investigational product administration
  - Concomitant medications/therapies survey
  - · Adverse events survey
  - Efficacy endpoints survey
    - NCI-CTCAE
      - i) The worst condition noted between the preceding evaluation (excluding any unscheduled evaluation) and the day of evaluation
      - ii) Condition at the time of evaluation
    - DEB-NTC

- FACT/GOG-NTX-12
- FACT-G\*1
- NRS (pain)
- Pregnancy test (only subjects for whom the test is required)\*2
- Vital sign measurement
- Laboratory tests (blood/urine)\*3
- Weighing of subject to determine investigational product dose\*3
- > Investigational product administration and administration status survey
- ➤ After investigational product administration
  - Postoperative adjuvant chemotherapy administration and administration status survey
  - · Adverse events survey
    - \*1 To be performed only in Courses 5 and 9
    - \*2 To be performed only in Course 2; may be determined on the day before Day 1
    - \*3 May be determined on the day before Day 1

# 9.2.2.6 Days 2 and 3 of Courses 2 to 12

- ➤ Before investigational product administration
  - Concomitant medications/therapies survey
  - Adverse events survey
  - Efficacy endpoint survey
    - NCI-CTCAE: The worst condition noted between the preceding evaluation (excluding any unscheduled evaluation) and the day of evaluation
- > Investigational product administration and administration status survey
- > Fluorouracil continuous intravenous infusion status survey
- > After investigational product administration
  - Blood sampling for pharmacokinetic analysis\*1
  - · Adverse events survey
    - \*1 To be performed once in any of Courses 2 to 12 if blood is not sampled in Course 1

